5 SAMPLE SIZE AND POWER

The sample size of the study is mainly determined by the feasibility concern. The study plans to enroll 200 participants; approximately 100 in Cohort 1, 50 in Cohort 2, 25 in Cohort 3, and 25 in Cohort 4 (approximately 100 in Cohort 1 and 100 in Cohorts 2-4 combined). Enrollment in Cohort 1 for participants with a favorable risk score will be capped at 25% of the total population to be enrolled in that cohort.

In general, the combination of nivolumab and ipilimumab has higher rates in IMAE of high grade (Grade 3-4) than nivolumab monotherapy. Study CA209016 reports that both combination treatment arms have approximately 40-60% high grade IMAEs (34.0% in N3+I1 arm and 63.8% in N1+I3 arm); Study CA209012 (for NSCLC) reports approximately 35% high grade IMAEs in both combined therapy arms. Given these reported values, the precision of half width of 95% confidence interval (CI) of AE rates is between 9.3% and 9.8% for 100 participants and between 6.6% and 6.9% for 200 participants pooled together. These precisions are deemed as acceptable in evaluating the research hypotheses with respect to study cohorts in terms of AE rates in the range reported by previous studies.

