7.1 General Methods

In general, unless expressly stated otherwise, all analyses will be performed by separated Cohort 1, Cohort 2, Cohort 3 and Cohort 4. Except where otherwise stated in this SAP, all analyses and summaries will be performed for all treated subjects. Analyses based on the combination of Cohorts 2-4 are considered not necessary for CSR as Cohort 4 has low KPS and tolerability may not be the same with other groups.

Unless otherwise noted, the bulleted titles in the following subsections describe tabulations of discrete variables, by the frequency and proportion of subjects falling into each category, by cohorts (with total). Percentages given in these tables will be rounded and, therefore, may not always sum to 100%. Continuous variables will be summarized by cohort (with total) using the mean, standard deviation, median, minimum and maximum values.

Time to event distribution (i.e. progression free survival, overall survival and duration of response) will be estimated using Kaplan Meier (KM) techniques. When appropriate, the median along with 95% CI will be provided using Brookmeyer and Crowley methodology (using log-log transformation for constructing the confidence intervals). Rates at fixed timepoints (e.g. PFS 1 at 6 months) will be derived from the Kaplan Meier estimate and corresponding confidence interval will be derived based on Greenwood formula for variance derivation and on log-log transformation applied on the survivor function $S(t)$.

The CA209 Core Safety DPP refers to several analyses that are to be performed on subjects with extended follow-up. For these summaries, AEs occurring from the time of the first dose of study therapy through 100 days after the last dose of study therapy will be summarized. Further general methods information for the safety analyses, including general methods for AEs and laboratory tests can be found in Section 7.1 of the IO core SAP.

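### The precision in SAP 5 fits only Cohort 1 among the cohorts as reported; Cohorts 2, 3 and 4 have intervals 1.4 to 2 times as wide, and no interval is planned for the primary rate

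*SAP*

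**What the plan says.** On size, SAP 5 states: "The sample size of the study is mainly determined by the feasibility concern". It plans about 100 subjects in Cohort 1, 50 in Cohort 2, and 25 each in Cohorts 3 and 4, and notes that Cohorts 2-4 together also make about 100. From high-grade IMAE rates reported in earlier combination studies (34.0% to 63.8%), it derives half-widths "between 9.3% and 9.8% for 100 participants and between 6.6% and 6.9% for 200 participants pooled together". It concludes: "These precisions are deemed as acceptable in evaluating the research hypotheses with respect to study cohorts".

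On the unit of analysis, SAP 7.1 says that "all analyses will be performed by separated Cohort 1, Cohort 2, Cohort 3 and Cohort 4", unless stated otherwise. It adds: "Analyses based on the combination of Cohorts 2-4 are considered not necessary for CSR". The reason given is that "Cohort 4 has low KPS and tolerability may not be the same with other groups". Discrete variables are tabulated "by the frequency and proportion of subjects falling into each category, by cohorts (with total"), so there is an all-cohort total column but no column for Cohorts 2-4 combined.

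On the primary endpoint, SAP 7.6.1.1 provides a count and percentage of treated subjects with a Grade 3-5 IMAE, tabulated by worst grade, system organ class and preferred term. It names no confidence interval. SAP 7.5.1.2 gives the objective response rate, a secondary endpoint, an exact Clopper-Pearson interval. For further AE methods SAP 7.1 refers elsewhere: "general methods for AEs and laboratory tests can be found in Section 7.1 of the IO core SAP".

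**The concern.** SAP 5 and SAP 7.1 do not describe the same groups. Of the two sizes for which SAP 5 quotes precision, 100 fits Cohort 1 but none of the other three cohorts, and 200 fits only a total that mixes two dosing regimens. The second primary objective (SAP 3.1) concerns the non-clear-cell, brain-metastasis and KPS 50-60% populations, and SAP 5 has no figure at their sizes.

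The primary endpoint is a descriptive rate with no hypothesis test. What the trial can say about each special population is therefore that rate and how uncertain it is. A reader who takes SAP 5 at its word would expect about ±10 points for Cohorts 3 and 4, when the value is about ±20. The primary table as described in SAP 7.6.1.1 would not show the difference, because no interval accompanies the percentage.

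**Working it through.** **Inputs.** Rates p from 0.34 to 0.638 (SAP 5; the range contains 0.50, where the half-width is largest). Confidence level 95%, taken as two-sided. Sizes 100, 50, 25 and 25, total 200 (SAP 5).

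**Step 1: reproduce SAP 5.** Normal approximation: half-width = 1.96 × √(p(1−p)/n).

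- n = 100: 1.96 × √(0.34 × 0.66/100) = 9.28 points; at p = 0.50, 1.96 × √(0.25/100) = 9.80; at p = 0.638, 9.42. Range 9.3 to 9.8, as stated.
- n = 200: 6.57 at p = 0.34, 6.93 at p = 0.50 and 6.66 at p = 0.638. Range 6.6 to 6.9, as stated.

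The arithmetic in SAP 5 is correct.

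**Step 2: the same formula at the other cohort sizes.**

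- n = 50: 1.96 × √(0.34 × 0.66/50) = 13.13; at p = 0.50, 13.86. The ratio to n = 100 is √(100/50) = 1.41.
- n = 25: 1.96 × √(0.34 × 0.66/25) = 18.57; at p = 0.50, 19.60. The ratio to n = 100 is √(100/25) = 2.00.

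**Step 3: exact intervals.** For x events in n, the Clopper-Pearson lower limit is the 0.025 quantile of Beta(x, n−x+1) and the upper limit is the 0.975 quantile of Beta(x+1, n−x). The half-width is (upper − lower)/2, taken over every integer x with 0.34 ≤ x/n ≤ 0.638.

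| Group | n | Counts | Normal approx. (points) | Exact (points) | Exact, ratio to n = 100 |
|---|---|---|---|---|---|
| All-cohort total | 200 | 68 to 127 | 6.6-6.9 | 6.8-7.1 | – |
| Cohort 1 | 100 | 34 to 63 | 9.3-9.8 | 9.7-10.2 | 1 |
| Cohort 2 | 50 | 17 to 31 | 13.1-13.9 | 13.8-14.5 | 1.4 |
| Cohorts 3 and 4, each | 25 | 9 to 15 | 18.6-19.6 | 19.8-20.4 | 2.0 |

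At n = 25 no count gives exactly 34.0% or 63.8%. The counts inside the range are 9/25 (36%) to 15/25 (60%).

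**Step 4: what this means for an observed rate near the bottom of the range.**

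- 34/100 (34%): exact interval 24.8% to 44.2%.
- 17/50 (34%): 21.2% to 48.8%.
- 9/25 (36%): 18.0% to 57.5%.

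**Step 5: sensitivity to cohort size.** The study design note calls all sizes approximate and allows for Cohorts 3 and 4 falling short. At assumed sizes the exact half-widths are 21.9 to 22.8 (n = 20), 18.1 to 18.7 (n = 30), 15.5 to 16.2 (n = 40) and 12.6 to 13.2 (n = 60).

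**The case against.** SAP 5 repeats protocol 10.1, and protocol 10.3 planned analyses for Cohort 1 and for Cohorts 2-4 combined. Both of those groups have about 100 subjects, so the precision statement suited the design it was written for, and its figures are right. Feasibility set the sample size, so new half-widths change no hypothesis, decision rule or enrolment target. That all stands. It explains the mismatch but does not remove it: the current SAP still makes an acceptability claim about cohorts that three of its four reported cohorts do not meet.

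On the missing interval, the SAP's document history records that the Clopper-Pearson interval was taken out of the primary analysis on purpose, and protocol 10.3.2 names none. A count and percentage is also the SAP's default for discrete variables, and any reader can compute an exact interval from them. This too is conceded: there is no oversight and no breach of the protocol. But SAP 5 justifies the trial by the width of an interval that the primary analysis, as described, does not report. The response rate, from which an interval is just as easy to derive, keeps one.

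The IO Core SAP and the Data Presentation Plan (SAP 7.1 and 9.1) are not available here and might call for an interval. The recorded removal makes that less likely but does not exclude it.

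Finally, adding normal-approximation figures for 50 and 25 would be enough to repair SAP 5. That is a fair alternative, provided the method is named.

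**Conclusion.** The concern holds. Among the cohorts as reported, the half-width for 100 subjects applies to Cohort 1 only. Cohort 2 is about 1.4 times as wide and Cohorts 3 and 4 about twice as wide: 13.8 to 14.5 and 19.8 to 20.4 points on the exact basis, against 9.7 to 10.2 for Cohort 1. The normal approximation gives the same ratios. The primary rate has no planned interval in the SAP text.

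This rests on the planned sizes being met, on true rates within the 34.0% to 63.8% range that SAP 5 cites, and on the two unseen documents not supplying an interval. Point estimates are unaffected. The weakness lies in the stated precision and in how the primary result is shown, and it should be corrected.

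**What to change.** 1. **SAP 7.6.1.1.** Add: *For each of Cohorts 1, 2, 3 and 4, the count and percentage of treated subjects with a Grade 3-4 or Grade 5 IMAE will be accompanied by a two-sided 95% exact (Clopper-Pearson) confidence interval.*

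2. **SAP 5.** Replace the precision statement with one on the same exact basis: *For observed rates from 34.0% to 63.8%, the half-width of the two-sided 95% exact interval is 9.7 to 10.2 percentage points for 100 participants (Cohort 1), 13.8 to 14.5 for 50 (Cohort 2) and 19.8 to 20.4 for 25 (Cohorts 3 and 4 each; counts 9 to 15). For 200 participants it is 6.8 to 7.1 and applies to the all-cohort total only. Cohort sizes are approximate.* Then state whether these per-cohort figures are acceptable.

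If the normal-approximation figures are kept, label them as such and give 9.3 to 9.8, 13.1 to 13.9 and 18.6 to 19.6 for the cohorts and 6.6 to 6.9 for the total.

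The cost is SAP wording and one table column. No protocol change, extra patients or new data are needed. The stated precision becomes less favourable for Cohorts 2-4 and, on the exact basis, slightly less favourable for Cohort 1 and the total.

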6 STUDY PERIODS, TREATMENT REGIMENS AND POPULATIONS FOR ANALYSES

6.1 Study Periods

The Baseline period and the Post-baseline period will be defined as detailed in Section 6.1 of the IO Core SAP.

6.2 Treatment Regimens

Refer to the [Section 2.1](#) for treatments subject receiving in each cohort.

6.3 Populations for Analyses

The following analysis populations are defined for this study:

- Enrolled subjects: All subjects who signed an informed consent form and were registered into the IVRS.
- Treated subjects: All subjects who received any nivolumab. This is the primary population for safety and efficacy analyses.

- Response evaluable subjects: All treated subjects who have baseline and at least one on-study evaluable tumor measurement. Refer to the efficacy analysis section for the analyses conducted on this population.
- Intermediate/Poor Risk Subjects: All Treated subjects with baseline IMDC prognostic score ≥ 1 (IVRS).
- Favorable Risk Subjects: All Treated subjects with baseline IMDC prognostic score = 0 (IVRS)
- PD-L1 treated subjects: All subjects with a PD-L1 assessment at baseline who received any dose of study therapy.

7 STATISTICAL ANALYSES

SAS® version 9.2 or higher will be used for statistical analyses, tabulations and graphical presentations.

7.1 General Methods

In general, unless expressly stated otherwise, all analyses will be performed by separated Cohort 1, Cohort 2, Cohort 3 and Cohort 4. Except where otherwise stated in this SAP, all analyses and summaries will be performed for all treated subjects. Analyses based on the combination of Cohorts 2-4 are considered not necessary for CSR as Cohort 4 has low KPS and tolerability may not be the same with other groups.

Unless otherwise noted, the bulleted titles in the following subsections describe tabulations of discrete variables, by the frequency and proportion of subjects falling into each category, by cohorts (with total). Percentages given in these tables will be rounded and, therefore, may not always sum to 100%. Continuous variables will be summarized by cohort (with total) using the mean, standard deviation, median, minimum and maximum values.

Time to event distribution (i.e. progression free survival, overall survival and duration of response) will be estimated using Kaplan Meier (KM) techniques. When appropriate, the median along with 95% CI will be provided using Brookmeyer and Crowley methodology (using log-log transformation for constructing the confidence intervals). Rates at fixed timepoints (e.g. PFS 1 at 6 months) will be derived from the Kaplan Meier estimate and corresponding confidence interval will be derived based on Greenwood formula for variance derivation and on log-log transformation applied on the survivor function $S(t)$.

The CA209 Core Safety DPP refers to several analyses that are to be performed on subjects with extended follow-up. For these summaries, AEs occurring from the time of the first dose of study therapy through 100 days after the last dose of study therapy will be summarized. Further general methods information for the safety analyses, including general methods for AEs and laboratory tests can be found in Section 7.1 of the IO core SAP.

7.2 Study Conduct

7.2.1 Accrual

The accrual pattern will be summarized per country, investigational site, and per month for all enrolled subjects. Enrollment date, first dosing date, country, investigational site will be presented in a by subject listing of accrual.

7.2.2 Relevant Protocol Deviations

The relevant protocol deviations will be summarized for all treated subjects. The following programmable deviations from inclusion and exclusion criteria will be considered as relevant protocol deviations. Non-programmable relevant eligibility and on-treatment protocol deviations, as well as significant (both programmable and non-programmable) eligibility and on-treatment protocol deviations will be reported through CTMS listings.

Eligibility at entrance:

1. Subjects having a baseline KPS less than 70% for Cohort 1, 2, and 3 or a baseline KPS no equal to 50-60% for Cohort 4
2. Subjects without extracranial metastasis as measurable disease

On-Study:

3. Subjects receiving antineoplastic therapy while on study therapy for a reason other than to treat a drug-related AE (i.e., chemotherapy, hormonal therapy, immunotherapy, extensive, non-palliative radiation therapy, or standard or investigational agents for treatment of RCC)

A by-subject listing of relevant protocol deviation will also be produced.

7.3 Study Population

7.3.1 Subject Disposition

Number of subjects enrolled, treated, not treated and reasons for not treated will be summarized for all enrolled subjects. Number of subjects who discontinued treatment, discontinued study, and reasons for these discontinuations will be tabulated by cohorts.

Subject disposition will be listed for all enrolled subjects. For subjects who are treated, the subject's gender, age, race, consent date, first and last dosing date, study discontinuation date, and reason for treatment discontinuation and study discontinuation will be listed for Treated subjects. For subjects who were enrolled but not treated, the subject's gender, age, race, consent date, and reason for not being treated will be listed.

7.3.2 Demographic and Baseline Characteristics

The following baseline characteristics will be summarized for all treated subjects, according to the general methods. All baseline presentations will identify subjects with missing measurements. Listings will also be provided.

- Age (descriptive statistics)
- Age (< 65, ≥ 65 - < 75, ≥ 75, ≥ 65)

- Gender (male, female)
- Race
- Ethnicity
- Child Bearing Potential Status
- Weight (descriptive statistics)
- Height (descriptive statistics)
- Baseline ECG
- Enrollment Cohort (1, 2, 3, 4)
- Baseline KPS (100, 90, 80,70, <70)
- Baseline IMDC prognostic score (0, 1-2, 3-6) (source: CRF)
- Smoking status (Never, Current, Former, Unknown)
- Disease stage at initial diagnosis (Stage I, II, III, IV)
- Time from initial disease diagnosis to date of first dose (< 1 year, >= 1 year)
- Disease stage at study entry (Stage III, Stage IV)
- Hemoglobin (<LLN, ≥ LLN)
- Corrected Calcium (≤ 10 mg/dl, >10mg/dl)
- Absolute Neutrophil count (>ULN, ≤ULN)
- Platelet count (>ULN, ≤ULN)
- Cell type (Clear Cell RCC, Non-Clear Cell RCC)
- All lesions (Tumor assessments at baseline): sites of disease, number of disease sites per subject.
- Target lesions (Tumor assessments at baseline): presence of target lesions, measurement of largest target lesion, site of target lesion, sum of target lesion diameters.
- Baseline PD-L1 expression
- Brain Metastases (Yes/No)
- Sarcomatoid Features (Yes/No)
- Histological subtypes (Papillary, Chromophobe, Translocation Associated, Collecting duct, Medullary, any pathogen unclassified, only for Cohort 2)

7.3.3 Medical History

General medical history will be listed by subject and pretreatment events will be tabulated by worst CTCAE grade and by system organ class (SOC)/ preferred term (PT) for all treated subjects.

7.3.4 Prior Therapy Agents

The following will be summarized by cohorts for all treated subjects, according to the general methods:

- Prior systemic cancer regimen (yes/no)
- Prior systemic therapy regimen setting (adjuvant/ neo-adjuvant/metastatic)

- Prior radiotherapy (yes/no)
- Prior surgery related to cancer (yes/no)
- Prior systemic therapy by setting and generic name.
- Prior/current other medication classified by anatomic and therapeutic classes.

Medication will be reported using the generic name. Listings of prior systemic cancer therapy, prior radiotherapy and prior surgery related to cancer, prior/current medications by subject will also be provided.

7.3.5 Baseline Examinations

Subjects with abnormal baseline physical exam results will be tabulated by examination criteria (eg, neck, cardiovascular, lungs, etc) for all treated subjects, according to the general methods.

7.4 Extent of Exposure

7.4.1 Administration of Study Therapy

The following parameters will be summarized (descriptive statistics) for all treated subjects, according to the general methods:

- Number of combined doses received (nivolumab + ipilimumab). A subject will be considered to have received combined doses of ipilimumab and nivolumab, if both infusions are administered on the same date.
- Number of doses received (nivolumab and ipilimumab)
- Cumulative dose (nivolumab and ipilimumab) in mg or mg/kg
- Relative dose intensity (%) using the following categories: < 50%; 50 - < 70%; 70 - < 90%; 90 - < 110%; ≥ 110%. (nivolumab and ipilimumab)

Table 7.4.1-1: Selection and Timing of Dose

Study Treatment	Unit Dose Strength(s)/Dosage Level(s)	Dosage Formulation Frequency of Administration	Route of Administration
Cohort 1	Nivolumab 6 mg/kg Ipilimumab 1 mg/kg Nivolumab 480 mg	Combination: D1W1 and then every 8 weeks. Monotherapy beginning D1W5 of C1, and then every 8 weeks	Nivolumab IV Ipilimumab IV
Cohort 2, 3, and 4	Nivolumab 3 mg/kg Ipilimumab 1 mg/kg Nivolumab 480 mg	Combination therapy: every 3 weeks for 4 doses. Maintenance monotherapy every 4 weeks afterwards.	Nivolumab IV Ipilimumab IV

Table 7.4.1-2: Study Therapy Parameter Definitions

	Cohort 1		Cohort 2, 3 and 4	
	Nivolumab	Ipilimumab 1 mg/kg	Nivolumab	Ipilimumab 1 mg/kg
Actual Dose (mg)	Actual dose is defined as the total dose delivered (mg) within each dosing visit.	Actual Dose (mg) is defined as the total dose delivered (mg) within each dosing visit.	Actual dose is defined as the total dose delivered (mg) within each dosing visit.	Actual Dose (mg) is defined as the total dose delivered (mg) within each dosing visit.
Actual Dose Level (mg/kg)	Actual Dose Level (mg/kg) is defined as the actual dose delivered (mg) within a dosing visit /most recent weight (kg) at the dosing visit.	Actual Dose Level (mg/kg) is defined as the actual dose delivered (mg) within a dosing visit /most recent weight (kg) at the dosing visit.	Actual Dose Level (mg/kg) is defined as the actual dose delivered (mg) within a dosing visit /most recent weight (kg) at the dosing visit.	Actual Dose Level (mg/kg) is defined as the actual dose delivered (mg) within a dosing visit /most recent weight (kg) at the dosing visit.
Cumulative Dose (mg/Kg)	Cumulative Dose (mg/kg) is the sum of the actual dose levels administered to a subject during the study.	Cumulative Dose (mg/kg) is the sum of the actual dose levels administered to a subject during the study.	Cumulative Dose (mg/kg) is the sum of the actual dose levels administered to a subject during the study.	Cumulative Dose (mg/kg) is the sum of the actual dose levels administered to a subject during the study.
Cumulative Dose (mg)	Cumulative Dose (mg) is the sum of the actual doses administered to a subject during the study.	Cumulative Dose (mg) is the sum of the actual doses administered to a subject during the study.	Cumulative Dose (mg) is the sum of the actual doses administered to a subject during the study.	Cumulative Dose (mg) is the sum of the actual doses administered to a subject during the study.
Total Expected Dose (mg)	$[6 \times \text{Weight}^* \times (\text{Last dose date of } 6\text{mg/kg} - \text{Start dose date of } 6\text{mg/kg} + 56)/56]$ + $[480 \times (\text{Last dose date of } 480 \text{ mg} - \text{Start dose date of } 480 \text{ mg} + 56)/56]$ *Average weight during 6 mg/ kg dosing is used.	$[1 \times \text{Weight}^* \times (\text{Last dose date} - \text{Start dose date} + 56)/56]$ *Average weight during 1 mg/ kg dosing is used.	$[3 \times \text{Weight}^* \times (\text{Last dose date of } 6\text{mg/kg} - \text{Start dose date of } 6\text{mg/kg} + 21)/21]$ + $[480 \times (\text{Last dose date of } 480 \text{ mg} - \text{Start dose date of } 480 \text{ mg} + 28)/28]$ *Average weight during 3 mg/ kg dosing is used.	$[1 \times \text{Weight}^* \times (\text{Last dose date} - \text{Start dose date} + 21)/21]$ *Average weight during 1 mg/ kg dosing is used.

Table 7.4.1-2: Study Therapy Parameter Definitions

	Cohort 1		Cohort 2, 3 and 4	
	Nivolumab	Ipilimumab 1 mg/kg	Nivolumab	Ipilimumab 1 mg/kg
Relative Dose Intensity (%)	Cumulative Dose (mg) x100/ Total Expected Dose (mg)	Cumulative Dose (mg) x100/ Total Expected Dose (mg)	Cumulative Dose (mg) x100/ Total Expected Dose (mg)	Cumulative Dose (mg) x100/ Total Expected Dose (mg)
Duration of Treatment	Last dose date - Start dose date +1. Last dose date is the last date subject received Nivolumab 6 mg/kg or 480 mg.	Last dose date - Start dose date +1	Last dose date - Start dose date +1. Last dose date is the last date subject received Nivolumab 3 mg/kg or 480 mg.	Last dose date - Start dose date +1

Duration of treatment will be presented using a Kaplan-Meier curve whereby the last dose date will be the event date for those subjects who are off study therapy. Median duration of treatment and associated 95% CI will be provided. Subjects who are still on study therapy will be censored on their last dose date.

A by-subject listing of dosing of study medication (record of study medication, infusion details, and dose changes) and a listing of drug assignment and dispensation will be also provided.

